Informed by our non-human primate (NHP) data, we will identify electrophysiological biomarkers related to the pre-ictal state and determine the influence of specific patterns of stimulation on these biomarkers. The results obtained here will be used to inform an early feasibility study of ADMES neuromodulation in patients using an implantable neurostimulation device (for which a separate IRB proposal will be submitted).

Study Endpoints

Each biomarker (or log biomarker) determined in the parameter sweep experiment will be estimated and compared by epileptic state using repeated measures analyses implemented via the SAS Procedure MIXED. Free recall accuracy will be statistically compared using a paired t-test between the ADMES and non-stimulation lists to determine whether there is any effect of ADMES on long-term memory.

Study Design and Methods

Electrode placement

Electrodes are implanted stereotactically to help localize the seizure focus. As a standard means to increase accuracy, the surgery is guided by contrasted MR images, with post-operative reimaging for confirmation. The electrodes (Dixi Medical or Adtech) have platinum contacts for electrophysiological (electroencephalogram [EEG] and local field potential [LFP]) recording and for stimulation). An electrode may include macroelectrode contacts only or macro- and micro electrode contacts. All electrodes are FDA-approved equipment for recording intracranial EEG during presurgical evaluation.

Monitoring Participants

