We have proposed an electric Wada test to be used to evaluate the safety of stimulation in the human following the parameters of the current UG3 grant.

This procedure will follow the protocol of the well-established Medical College of Georgia (MCG) Wada (behavioral) procedure used with the setting of the intracarotid amobarbital procedure (10). This protocol was designed to introduce novel objects, which could be dually encoded by visual and verbal means during a period of drug anesthesization, with an evaluation of recognition memory to occur after the effects of the drug had cleared. The period of delay tended to average 10 to 15 minutes in this chemical procedure. We will follow the exact same behavioral protocol while replacing the administration of drug with the administration of electrical stimulation. As we are more interested in determining any effect on function, we will apply stimulation during the entire test session (i.e., encoding through recall) rather than just during encoding.

We will establish a baseline with each potential subject by testing them during a period free of electrical stimulation. They will be presented with a set of 8 real objects, presented one at a time in sequential order, while being provided with the name of each object orally in simultaneous fashion (e.g., "remember the fork" when being presented with an actual fork). After all 8 objects are presented, we will have the patient engaged in another task for 15 minutes, and then ask them to freely recall all 8 objects. Next, we will show them the 8 objects intermixed with 16 similar foils, and have them respond "yes" or "no" as to whether or not they have been shown each object. We are primarily interested in the recognition recall score, consistent with the use of the aforementioned chemical Wada.

The same procedure will be used with a different set of objects during the application of stimulation. We will complete two trials at the highest tolerable frequency of stimulation using both asynchronous and continuous stimulation. The encoding phase will likely require approximately one minute. After the novel objects are presented to the subject, they will be asked to engage in additional tasks during the 15-minute delay period. We

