will have them perform standard clinical tasks of attention and processing speed during the delay period (e.g., Digit Span, Coding tasks, verbal fluency), as these are tasks that could be affected by stimulation (i.e., tasks of general function that are affected by any general disruption in brain function). Following the delay period, the subject will be asked to recall the 8 target objects, and their verbal responses will be recorded. We will calculate their total score and any false positive errors. Next, we will show the subject the 8 objects intermixed with 16 similar foils, and we will have them respond "yes" or "no" as to whether or not they have been shown each object. This will allow us to calculate scores that reflect the total number of accurate identifications (i.e., total "hits" out of 8) a total number of false positive errors, and a corrected score (i.e., half a point will be deducted from the total hits for each false positive error made).

We will create three sets of objects for this procedure, so that it can be repeated to obtain a baseline as well as to test the asynchronous and continuous stimulation parameters.

Procedures Involved

Clinical assessments

Prior to enrollment in the study, all patients will have had a standard presurgical workup, including video EEG monitoring, brain MRI, PET scan, neuropsychological testing, and functional MRI or Wada (sodium amobarbital) test. As part of their presurgical workup, they will require an intracranial electrode study (stereoelectroencephalography, SEEG) for further seizure focus localization, with multiple hippocampal electrode arrays, either unilaterally or bilaterally.

Patients will be admitted to the hospital for surgical implantation of depth electrodes. After electrode placement and confirmation of electrode location with imaging, patients will be monitored with continuous intracranial EEG recording in the Emory Epilepsy Monitoring Unit. Post-operative imaging (CT or MRI) is used to confirm location of the electrodes. Their seizure medications will be lowered, directed by the epilepsy team, in order to capture and characterize habitual seizures. This "seizure capture" phase typically lasts 7-21 days, with minimum of 3-5 clinical seizures captured during this time.

Prior to the Testing Session

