We are not studying a vulnerable group and will not include children, incarcerated persons, persons with cognitive disability or persons who are unable to give consent.

Local Number of Participants

Based on our power analysis, we estimate needing about 18 subjects for our analysis. Other studies in our Unit have typically had consent rates of 80% for eligible patients. We admit about 50 patients per year for intracranial EEG monitoring, with approximately 50% having mesial temporal lobe epilepsy.

Recruitment Methods

All patients entering our Intracranial Monitoring Unit who meet inclusion criteria will be approached for potential participation after recovery from the implantation surgery (>= 72 hours after implantation).

Patients with refractory suspected MTLE undergoing sEEG represent an accessible patient population from which participants may be recruited. As a high volume tertiary care epilepsy center (14 epileptologists, 3 nurse practitioners, and 2 epilepsy neurosurgeons), the Emory Epilepsy Center has unparalleled access to a large and continuously growing population of patients with refractory epilepsy. Emory is the only Level IV epilepsy center (including an active epilepsy surgery program) in the greater Atlanta area (a city of > 6 million people). Atlanta has one of the largest African American populations of any metropolitan area in the United States. 36% of the patients seen in the Emory Epilepsy Clinic are African American, and 56% of the patients seen are women.

Based on our past clinical volume, we estimate that >20 patients with MTLE will undergo SEEG per year. Study subjects will be recruited from this pool of patients. Our recruitment and retention rates for current and recent research protocols in SEEG patients have been ~80%. We are targeting to enroll 18 subjects, which should be feasible given our historic volume and recruitment rates.

Withdrawal of Participants

If the patient requests to withdraw from the study, all research and clinical records maintained outside the clinical record will be erased, with documentation of the original consent and that the subject has withdrawn from the study.

Risks to Participants

Referred Pain from Meningeal and Large Vessel Stimulation. This is unlikely to occur during hippocampal stimulation, but can be minimized and is not uncomfortable when stimulation intensity is increased gradually.

Seizure

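### The electric Wada is given a safety purpose, but the only memory analysis stated is a group-mean t-test that would usually miss a large loss in one to three of 18 patients

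*Combined protocol and SAP*

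**What the plan says.** Under ADMES effects on memory, the purpose is stated first: "We have proposed an electric Wada test to be used to evaluate the safety of stimulation in the human". Each patient is tested once without stimulation, then with asynchronous and with continuous stimulation: "We will create three sets of objects for this procedure, so that it can be repeated to obtain a baseline", with the other two sets for the stimulated trials. Each trial has 8 target objects, free recall after a 15-minute delay, then yes/no recognition with 16 foils. On the score that matters, the section says: "We are primarily interested in the recognition recall score, consistent with the use of the aforementioned chemical Wada". It also defines a corrected recognition score, in which "half a point will be deducted from the total hits for each false positive error made". It gives no test, margin or threshold for any of these scores.

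The one memory analysis is under Study Endpoints: "Free recall accuracy will be statistically compared using a paired t-test between the ADMES and non-stimulation lists to determine whether there is any effect". The outcome meant there is long-term memory. Local Number of Participants says: "Based on our power analysis, we estimate needing about 18 subjects for our analysis". That power analysis is not shown, so the significance level, power, effect size, SD and powered endpoint are all unknown.

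**The concern.** A test with a safety purpose should show harm in an individual patient, or at least limit how large the average harm could be. The stated analysis does neither. A t-test for any mean difference averages a few large losses with many unchanged scores, and those same losses enlarge the SD in the denominator. Without a confidence limit, a non-significant result does not rule out a meaningful mean loss either.

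Each patient has a personal baseline, so individual change can be calculated, but no rule uses it. Patient-level rules do exist for afterdischarges and seizures, side-effects in threshold testing, anything the patient notices, distress during memory testing, and adverse events. None refers to a memory score.

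What is at stake is what the trial can say about memory. The Background says the results will inform an early feasibility study of ADMES with an implanted device.

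**Working it through.** **Inputs.** From the document: n = 18; 8 targets and 16 foils; half a point off per false positive; one baseline and two stimulated trials per patient. Assumed, because the document gives no value: two-sided 5% level (the test is for any effect); SD of the stimulated-minus-baseline difference in unaffected patients of 1 to 2 points; a loss of 5 points in k patients and no true change in the others.

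**The plan's own figure.** N = 18 cannot be reproduced, because none of its inputs is given. For orientation, a paired t-test with n = 18 has 80% power for a mean difference of 0.70 SD and 90% power for 0.81 SD (two-sided 5%).

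**Step 1, no noise.** If k of n patients lose L points and the rest do not change, the mean loss is kL/n and the SD is L × sqrt(k(n − k)/(n(n − 1))). Then t = mean/(SD/sqrt(n)) = sqrt(k(n − 1)/(n − k)). L cancels, so the result holds for any size of loss and on either score. With n = 18, t = sqrt(17k/(18 − k)), against a critical value of 2.11 on 17 degrees of freedom. For k = 3, t = sqrt(51/15) = 1.84.

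**Step 2, with noise.** Simulated share of trials with p < 0.05 for a 5-point loss:

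| Patients affected (k) | t, no noise | p, no noise | SD 1 | SD 1.5 | SD 2 |
|---|---|---|---|---|---|
| 1 | 1.00 | 0.33 | 3% | 4% | 5% |
| 2 | 1.46 | 0.16 | 7% | 9% | 8% |
| 3 | 1.84 | 0.083 | 18% | 17% | 15% |
| 4 | 2.20 | 0.042 | 41% | 33% | 26% |
| 5 | 2.56 | 0.020 | 71% | 53% | 41% |

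With no true loss the rate is 5%.

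**Step 3, sensitivity.** For losses of 4 to 7 points and SD 0.5 to 2, detection with three affected patients never exceeds 18%. Binomial scores out of 8 give 1–5%, 3–9% and 11–18% for k = 1, 2 and 3. A Wilcoxon signed-rank test (6-point loss, SD 1) gives 7% and 15% for k = 2 and 3, so a rank test does not help. A one-sided 5% test gives 24–65% for k = 3.

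**Step 4, precision.** The 95% half-width for the mean change is 2.11 × SD/sqrt(18), which is 0.50, 0.75 and 0.99 points for SD 1, 1.5 and 2. If no patient declines, the exact two-sided 95% upper limit on the decline rate is 1 − 0.025^(1/18) = 18.5%. With 2 of 18 declining, the exact interval is 1.4% to 34.7%.

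**Step 5, cost of a patient-level count.** Corrected recognition runs from 0 − 16 × 0.5 = −8 to 8, so six extra false positives cost 3 points with every target still recognised. With no true effect and normal noise, the chance of at least one apparent decline of c points among 18 patients is 1 − (1 − Φ(−c/SD))^18 per stimulated trial. For c = 3 this is 2%, 34% and 71% at SD 1, 1.5 and 2; for c = 2 it is 34%, 82% and 96%. Over two stimulated trials sharing one baseline (correlation 0.5), c = 3 gives 5%, 53% and 89%.

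**The case against.** The strongest reply is that the t-test is not stated to be the electric Wada's criterion. Study Endpoints speaks of free recall and of lists, which fits the free recall task named in the ADMES section. The Wada procedure uses object sets and puts recognition first. This stands, and it means that the score of primary interest has no stated analysis at all. The arithmetic applies to a group-mean test on either score.

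A reader might infer that the trial will declare stimulation safe for memory if the test is non-significant. The document does not say so. Aim 3 is to identify changes in memory, memory is a secondary objective, and the monitoring section likens the study to basic science. What remains is that a test with a declared safety purpose has no other rule.

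A reader might also infer that large losses make significance less likely in general. The table shows otherwise: against the 5% rate with no losses, detection is lower or about equal with one affected patient, slightly higher with two, and clearly higher from three.

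Two further points stand in part. The Background raises memory decline in connection with resective surgery, whereas the stimulation protocol speaks of temporary effects, so the two harms should not be equated. The section also defers to a published Wada procedure and to grant parameters, and whether these contain per-patient criteria cannot be checked here. Finally, a patient-level cut-off on a single baseline is noisy, as Step 5 shows. That calls for showing the error rate beside the count; it does not justify leaving the count out.

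**Conclusion.** The point holds within limits. The electric Wada has a safety purpose, its main score has no stated analysis, and the only memory test in the document is insensitive to severe loss in one to three of 18 patients: at least 82% of such trials would be non-significant in the scenarios examined. Detection rises from four to five affected patients, reaching 41% and 71% at SD 1, so the claim does not extend to widespread loss.

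These figures rest on an assumed two-sided 5% level, an assumed noise SD, and a loss confined to a few patients. A one-sided 5% test with little noise would detect three affected patients more often than not, but a test for any effect implies two sides.

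The document does not support saying that the trial will misreport safety. It supports saying that a non-significant result could not establish safety and that nothing else in the plan would. This should be corrected before the scores are reviewed.

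**What to change.** Keep the mean comparison and amend Study Endpoints and the memory section as follows.

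- Apply the paired comparison to the corrected recognition score as well as to free recall.
- For each stimulated trial, report the mean change from baseline with its 95% confidence interval, and list every patient's individual change.
- Report the number of patients whose score falls by at least an amount that the investigators fix before data review, with an exact 95% confidence interval. Choose that amount with the −8 to 8 range and test-retest noise in mind, and print the expected false-decline rate beside it, since there is only one baseline trial.
- State that a non-significant t-test alone is not evidence of memory safety.

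The cost is endpoint wording and one table from scores already collected, with no added patients or procedures. There are two downsides. The safety statement becomes less favourable, because even 0 of 18 declines cannot exclude a rate of up to 18.5%. Some of the declines counted will also be noise.

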Currently responsive neurostimulation (RNS, Neuropace, Inc) is the only FDA approved implantable neurostimulation device approved for neuromodulation directed at the hippocampus[3]. Recommended stimulation protocols include the use of high frequency (130-200 Hz) stimulation synchronized across implanted electrodes in response to detected seizures[5, 6]. In contrast, we have found that delivering asynchronous pulses distributed across a multi-electrode array of 16 micro-electrodes and stimulating at low (theta) frequencies is more effective than macrostimulation in controlling seizures in a rodent model of MTLE[7]. Asynchronous distributed multi-electrode stimulation (ADMES) can be delivered in a continuous fashion, but has the potential to be used in a responsive or optimized manner as well. These stimulation modes require the ability to identify biomarkers, or neurophysiologic features identifiable on recording on neural activity, indicative of impending seizures to optimize stimulation. The goal of the present study is to explore potential biomarkers that could distinguish between the interictal (between seizures), pre-ictal (before seizures) and ictal states (during seizures) to be used later for optimization of stimulation parameters in human subjects with implantable neurostimulation device.

As a high volume epilepsy surgery center, we have a unique opportunity to study electrophysiology directly from the brain in human subjects with epilepsy using electrodes already in place for clinical purposes. For many patients being considered for epilepsy surgery, invasive monitoring with stereo-EEG (SEEG) electrodes is needed to localize seizure onset zone. As part of routine clinical care, SEEG electrodes are used to monitor and record brain activity and for brain stimulation for the purpose of mapping brain function and eliciting seizures. During SEEG in patients with mesial temporal lobe epilepsy, depth electrode arrays are routinely placed in the hippocampus. We can utilize these implanted electrodes to both stimulate in an asynchronous manner and also simultaneously record local field potentials (LFPs) for analysis of biomarkers.

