Intracranial Electroencephalographic (iEEG) Activity: This study analyzes routine diagnostic EEG data that is generated using intracranial electrodes. The number, type, orientation, and size of the iEEG electrodes depend on the anatomy and clinical considerations per patient. Typically there will be tens to hundreds of electrode contacts arranged as a depth, strip, and/or grid. An electrode may be relatively large (macroelectrode) or very small (microelectrode). Macroelectrode local field potentials (LFPs) consist of 0.1-1000 Hz signals obtained from iEEG contacts placed either within the brain (i.e. recorded from depth electrodes) or on the surface of the brain (i.e. recorded from subdural strip or grid electrodes). These signals will be acquired at 256 or 512 samples per second and 12-bit precision for electronic storage. Both the standard and investigational macroelectrode iEEGs are automatically stored to a 2-Tetabyte RAID server that is securely managed by Emory Healthcare Information Services (EHc-IS). The stored data is directly accessed via only one password-protected Epilepsy Monitoring Unit EMU computer that is securely managed by EHc-IS. Microelectrodes record signals at a sampling rate of up to 30,000 samples per second and 16-bit precision for electronic storage. These signals are then processed by applying a high-pass filter between 100 and 750 Hz, in order to extract the extracellular action potential waveforms (single unit activity) from neurons located in the vicinity of the recording contact.

[figure not shown]

Figure 1: Schematic for study device in System 1.0 configuration. Here, the testing computer interfaces with the existing clinical EEG system via the Sync Box and stimulates via the CereStim.

[figure not shown]

Figure 2: Schematic for the study device in System 2.0 configuration. Here, a custom cable and splitter box connects the Blackrock NeuroPort and CereStim to the subject electrodes for data recording and stimulation.

Intracranial stimulation protocol

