We will schedule a time that is convenient for the patient to undergo testing, typically suggesting that a 1-2 -hour block of time is ideal. On the day of proposed testing, we will again check with the clinical team and patient that the originally proposed time and date is still acceptable.

Patient Instructions

General Instructions. The patient is asked to get comfortable and if they need to use the restroom or need anything to drink. The patient is asked to minimize head movement during the study, as well as to maintain wakefulness. During the majority of the sessions during which patient participation is not needed, they can watch television, read or talk to friends or family members that they permit to remain in the room. During stimulation, patient is continuously monitored clinically, as well as by EEG. If the patient notes anything they are to verbalize this or raise a hand. Stimulation is then immediately stopped

to discuss what was noted. A decision is then made about whether to persist with stimulation of the present electrodes or move to the next. The patient is able to stop the study at any time.

The Testing Session

Not including the time to set-up equipment, the actual testing session is expected to last \sim 1-2 hour and will not exceed four hours. The patient can take breaks during the session for food, rest, drink or bathroom use. The patient is at liberty to terminate the session at any time. Brain stimulation will be performed as detailed above.

Number of Sessions

Patients will undergo three ~1-2-hour testing sessions occurring on subsequent days.

Debriefing

The patient will be given the opportunity to ask questions of the team at any time, but will be invited to do so at the end of a session. This way, they can learn about what was tested and how this knowledge can lead to better patient outcomes or increased knowledge of brain function. We will not give medical advice during this de-brief and the study is not designed to provide information that is useful in relate to a specific patient's care. Where there is such information, this will be relayed to the clinical team.

Data and Specimen Banking

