 - The medical doctor for the patient holds primary responsibility for monitoring the safety of each subject both during study visits and in between study visits, if complications arise. All complications will be well documented, followed, and submitted to the Emory IRB and reported to the DSMB either annually or ad hoc.

The PIs, [name] and [name], will be primarily responsible for monitoring patient safety. Additionally, because this work is conducted in the Intracranial Monitoring Unit (ICMU) while each participant is hospitalized, the ICMU staff (including members of this study) and Emory HealthCare IT maintain strict EHC standards for patient confidentiality, safety and data storage. Each time a patient is included in the study, the PI will discuss the patient with both clinical staff and the study personnel involved in research to ensure that there was no additional risk to the patient, no adverse event and that the patient was safe.

If there are any concerns, these will be handled as required by the protocol. Any unanticipated problem or adverse event due to the study will be carefully documented, investigated and submitted to the Emory eIRB under Reportable New Information (RNI). The eRIB submission will also be shared with the DSMB. Copies of each report and documentation of IRB notification and receipt will be kept in the PI's study file.

Monitoring of the following information, and other pertinent permissible data, for study participants will occur continuously for the purposes of the Study Objectives and Safety Monitoring:

- Administrative and scheduling information
- Proper attainment and storage of signed informed consents
- Any adverse events
- Withdrawals from the study
- Experimental data
- Original and processed neurophysiological recordings (including video)
- Medical and surgical records before, during and after the present admission

• Any diagnostic testing pertaining to the patient's epilepsy, neurological status and present admission. neurophysiology or neuroimaging of the brain

Reporting

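### Biomarkers are compared by epileptic state alone while antiseizure drugs are being lowered, so interictal versus pre-ictal or ictal differences may partly reflect drug level

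*Combined protocol and SAP*

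**What the plan says.** Under Procedures Involved, Clinical assessments, patients have continuous intracranial EEG after implantation, and "Their seizure medications will be lowered, directed by the epilepsy team, in order to capture and characterize habitual seizures". This "phase typically lasts 7-21 days, with minimum of 3-5 clinical seizures captured during this time".

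The Background gives the goal as finding features that separate interictal, pre-ictal and ictal states. Under Study Endpoints, each biomarker from the parameter sweep experiment "will be estimated and compared by epileptic state using repeated measures analyses implemented via the SAS Procedure MIXED". No covariate is named.

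On the source of the recordings, the iEEG Activity paragraph says: "This study analyzes routine diagnostic EEG data that is generated using intracranial electrodes". Number of Sessions says: "Patients will undergo three ~1-2-hour testing sessions occurring on subsequent days". The Data and Safety Monitoring Plan lists among the monitored information "Medical and surgical records before, during and after the present admission", but gives these records no part in the analysis.

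The documents do not define an interictal or pre-ictal window. They do not say when such windows are taken relative to the drug lowering, or how far and how fast drugs are lowered. The two-hour seizure-free rule under Pre-stimulation threshold testing governs when a session may start and does not address drug level.

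**The concern.** Drug lowering is a planned influence on epileptic state, since its purpose is to obtain seizures. If it also moves local field potential features such as spectral power or synchrony, it is a common cause of state and biomarker. A repeated-measures model removes stable differences between patients. It does not remove an exposure that changes within a patient along with the state being compared.

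Finding pre-ictal biomarkers is Specific Aim 1. Those features are what the stimulation sweeps in Aim 2 try to modify, and the results are to inform a later implant study. A feature that partly tracks drug level could be carried forward as if it signalled an approaching seizure.

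**Working it through.** The plan gives no figure on this point to reproduce. The nearest is the sample size of 18, attributed to a power analysis whose effect size, SD, alpha and power are not stated.

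**1. Which recordings can supply pre-ictal windows?** Three sessions of 1-2 hours total 3-6 hours. The stay is 7-21 days (168-504 hours), with 3-5 seizures stated as a minimum. At an even seizure rate, the expected number per patient falling inside sessions is:
- low: 3 × 3/504 = 0.018
- high: 5 × 6/168 = 0.18

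Over 18 patients this is about 0.3 to 3. Pre-ictal windows must therefore come mostly from the stay-long recording, which agrees with the statement about routine diagnostic EEG.

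**2. How much of a drug effect enters the contrast?** Let x be the withdrawn fraction of drug. Assume that x rises linearly from 0 to 1 over the stay and that the seizure rate is proportional to 1 + kx. None of this is in the documents.
- Mean x over evenly spread interictal windows = 1/2.
- Mean x at seizures = (1/2 + k/3)/(1 + k/2).
- Difference = k/(12 + 6k).

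| Rise in seizure rate | k | Difference, taper to zero | Same rise, drugs only halved |
|---|---|---|---|
| two-fold | 1 | 1/18 = 0.056 | 0.028 |
| six-fold | 5 | 5/42 = 0.119 | 0.060 |
| no seizures at full dose | limit | 1/6 = 0.167 | 0.083 |

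If the two-fold or six-fold rise belongs to full withdrawal and only half the taper is reached, k falls to 0.5 or 2.5. The halved-drug figures become 0.5 × 0.5/15 = 0.017 and 0.5 × 2.5/27 = 0.046.

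If all interictal windows came from the first third of the stay, their mean x would be 1/6. The difference would then be 1/3 + k/(12 + 6k): 0.39, 0.45 and 0.50 for the three rows with a taper to zero.

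**3. Effect on false positives.** A simulation had no true state effect and used a nominal two-sided 5% test. Assumptions: 18 patients, a 10-day stay, a linear taper over the first 4 days, 4 seizures, a six-fold hazard at full taper, 20 interictal windows, a between-patient SD of 0.3 for the drug shift, 1,500 runs, and a paired t-test on patient means standing in for the mixed model. The drug shift is in within-patient SD units.

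| Interictal windows | No shift | Shift 0.5 SD | Shift 1.0 SD |
|---|---|---|---|
| Spread over the stay | 5.7% | 6.6% (bias 0.06 SD) | 12.4% (bias 0.11 SD) |
| First 2 days only | 6.5% | 62% (bias 0.33 SD) | over 99% (bias 0.66 SD) |
| Matched on drug level | 5.0% | 3.8% (bias about 0) | 5.1% (bias about 0) |

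Monte Carlo error is about 0.6 percentage points near 5%. The timing of interictal windows decides the result.

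**The case against.** The strongest reply is that the analysed data may not span the taper at all. The endpoint sentence ties the biomarkers to the parameter sweep, and sweeps are run in sessions on consecutive days. Inclusion criterion 3 requires onset already confirmed on SEEG, and patients are approached no sooner than 72 hours after implantation. Sessions therefore probably follow at least some drug lowering. This stands as a genuine ambiguity about timing. It does not settle the matter, because step 1 shows that sessions alone would yield almost no pre-ictal windows. If interictal windows came from sessions and pre-ictal windows from elsewhere in the stay, the imbalance would remain, in either direction.

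The second reply is that the effect may be small. It stands in part. With interictal windows spread over the stay and a 0.5 SD shift, 6.6% cannot be told apart from the no-shift runs. The documents describe drugs as lowered, not stopped, and these patients have refractory epilepsy, so the rows with a taper to zero or no seizures at full dose are upper ends.

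A reader might go further and infer either of two things:
- That stimulation effects drift with the taper across the three sessions. The protocol records before, during and after each stimulation, uses 5 seconds of stimulation with 10-20 seconds of washout, and randomizes the sweep. Drift over days barely moves within such a trial and is not aligned with the order of patterns.
- That the resulting biomarker would fail in outpatients on stable medication. Nothing in the documents shows this, and the search objective also draws on independent non-human primate work.

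**Conclusion.** The point holds in conditional form. The plan compares biomarkers by state alone while a within-patient exposure is being changed to bring about that state, and neither window selection nor the model deals with it. Whether this biases the interictal versus pre-ictal or ictal contrast depends on drug level shifting the features, which is assumed.

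Given such a shift, and on the step 2 assumptions, the contrast carries about 0.06 to 0.17 of the full-withdrawal effect when interictal windows are spread over the stay, and about half that or less if drugs are only halved. It is large if interictal windows come mainly from before the taper and near zero if they are matched. Pre-ictal versus ictal is little affected because the two are adjacent in time.

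It would be tempting to quote the 0.50 in step 2 as the size of the bias. That figure needs a taper to zero, no seizures at full dose and interictal windows only from the first third of the stay, and the protocol states none of these. What can be said firmly is that the protocol leaves open the choice that separates a negligible bias from a decisive one. That choice should be fixed before the windows are selected.

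**What to change.** Amend Study Endpoints, and leave medication management as it is:

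- **Matching.** Compare each pre-ictal or ictal window with interictal windows from the same patient at the same antiseizure dose step (a period of unchanged regimen), or from the same or an adjacent day. Prespecify a minimum gap from any seizure. Without that gap, same-day matching could admit post-ictal or pre-ictal recording as interictal.
- **Recording.** For each window, take drugs, dose and time since last dose from the admission record.
- **Sensitivity model.** Report a mixed model with dose as a time-varying covariate, or day of stay where the two are collinear. Prespecify how dose is coded for patients on several drugs.

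The cost is fewer eligible interictal windows per seizure and some chart abstraction. EEG recording is continuous and medical records from the admission are already monitored, so no new procedure for the patient is needed.
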